The primary endpoint is the pharyngeal cure rate – that is, the proportion of subjects who return for TOC who clear their infections as evidenced by a negative culture 4-7 (+/-1) days after treatment. Persons who test negative for NG at their enrollment visit (i.e. infection cleared between initial clinical screening test and enrollment) will be excluded from analysis. Treatment failure will be defined as a positive culture 4-7 (+/-1) days after treatment. The cure rate will be calculated as the number of cured subjects divided by the total number of subjects who received treatment and returned for follow-up testing in a modified an intention to treat (mITT) analysis. We will also calculate the 95% CI for this proportion.

We will conduct an interim analysis after we have primary outcome results for 25 subjects. If the cure rate is $\leq 44\%$ (99% CI 17% – 74%; i.e. 12 persons of 25 persons with a positive culture on treatment date fail treatment), we will stop the study. We will also monitor for renal toxicity at the interim analysis. We plan to obtain pre-treatment and post-treatment Creatinine. Increases $>40\%$ will be considered significant. If more than 20% of the study population has a $>40\%$ increase in serum Creatinine, we will halt the study. We chose 20% because if 20% of subjects experience renal toxicity it is unlikely to be due to chance (95% CI 7 – 40%). For our second objective, we will compare the MIC of cures to treatment failures using a stratified approach (Table 2), and we will correlate this data with individual peak gentamicin level in order to estimate the ideal pharmacodynamic (PD) criterion (Obj. 2). For persons who fail treatment we will also compare the pre- and post-treatment genatmicin MIC to estimate whether single dose gentamicin therapy can “induce” resistance (Obj. 3) as an exploratory analysis. We will consider an increase in the MIC by two doubling-dilutions (i.e. from MIC of 2 to 8 $\mu\text{g/mL}$, or 8 to 32 $\mu\text{g/mL}$) to represent induced resistance, and we will calculate the

proportion of isolates among those that fail treatment that demonstrate induced resistance following receipt of gentamicin. Lastly, we will report the number and proportion of subjects who report side effects.

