The Medical Monitor, [name], will review study conduct including efficacy and renal toxicity and AEs in aggregate on at a single interim analysis after 25 subjects, and at the end of the study. The Medical Monitor will review serious adverse events (SAEs), hearing loss, and serious drug allergies in real-time. Study data are provided to the Medical Monitor prior to the interim and final analysis. Data reports are prepared by the PI, [name].

MONITORING REPORT

The Medical Monitor, [name], will provide a written report to the study team with recommendations for study modification, study continuation/discontinuation as relevant. The study team is responsible for forwarding the report to the IRB.

COLLECTION AND REPORTING OF SAEs AND AEs

For this study, the following standard AE definitions are used:

Adverse event: Any unfavorable and unintended sign (including an abnormal laboratory finding), symptom or disease temporally associated with the use of a medical treatment or procedure, regardless of whether it is considered related to the medical treatment or procedure.

Serious Adverse Event: Any AE that results in any of the following outcomes:

- Death
- Life-threatening
- Event requiring inpatient hospitalization or prolongation of existing hospitalization
- Persistent or significant disability/incapacity

AEs are graded according to the following scale:

Mild: An experience that is transient, & requires no special treatment or intervention. The experience does not generally interfere with usual daily activities. This includes transient laboratory test alterations.

Moderate: An experience that is alleviated with simple therapeutic treatments. The experience impacts usual daily activities. Includes laboratory test alterations indicating injury, but without long-term risk.

Severe: An experience that requires therapeutic intervention. The experience interrupts usual daily activities. If hospitalization (or prolongation of hospitalization) is required for treatment it becomes an SAE.

The study uses the following AE attribution:

Not related: The AE is clearly not related to the study procedures (i.e., another cause of the event is most plausible and/or a clinically plausible temporal sequence is inconsistent with the onset of the event).

Possibly related: An event that follows a reasonable temporal sequence from the initiation of study procedures, but that could readily have been produced by a number of other factors.

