Related: The AE is clearly related to the study procedures.

AEs are identified at the TOC visit using the symptom screen, and with Creatinine monitoring.

SAEs and specific procedure-associated AEs are reported to the Medical Monitor within 24 hours. In addition, all AEs are reported according to the University of Washington AE reporting guidelines.

MANAGEMENT OF RISKS TO SUBJECTS

Expected AEs

Expected AEs associated with gentamicin include:

- Pain at injection site
- Bruising at injection site

AE Management

- Warm compresses as needed
- Tylenol as needed

DATA ANALYSIS PLANS

The Medical Monitor will conduct interim analyses after we have primary outcome results for 10 and 25 subjects. (Enrollment will pause until analyses can be conducted). Stopping rules include the primary end point (i.e. pharyngeal cure rate), and adverse events. If after 10 and 25 subjects, the cure rate is $\leq 44\%$ (99% CI 17% – 74%; i.e. 11 persons of 25 persons with a positive culture on treatment date fail treatment), we will stop the study. We chose these numbers using the O'Brien-Fleming method of alpha spending for multiple analyses, assuming an alpha of 0.003 for the first analysis and an alpha of 0.049 for the final analysis. Using the 99% CI obtained with 11/25 treatment failures, the upper bound is less than 75%. (Our hypothesis is that gentamicin alone will be 80% effective for pharyngeal gonorrhea, with the goal to use it in combination with a second agent). Alternatively, if at interim analysis more than 20% of subjects (99% CI 20% - 46%) have a greater than 40% increase in their creatinine from baseline, we will halt the study.

Data Analysis

The proposed study aims to evaluate the efficacy of a single intramuscular (IM) dose of 360 mg of gentamicin in the treatment of pharyngeal gonorrhea. Secondary objectives include evaluating the renal safety and tolerability of 360mg of gentamicin, *documenting peak serum gentamicin levels by subject weight*, and estimating the ideal pharmacodynamic criterion using a combination of peak gentamicin concentration levels compared to MIC and treatment outcomes. *In exploratory analyses*, we will attempt to determine whether gentamicin-monotherapy induces antimicrobial resistance among treatment failures. The specific aims are:

- 1) Determine the proportion of persons whose pharyngeal gonococcal infections are cured with a single dose of 360mg gentamicin intramuscularly alone.

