As a means to preserve funding and ensure safety, we will conduct interim analyses after we have primary outcome results for 10 and 25 subjects. (Enrollment will pause until analyses can be conducted). Stopping rules include the primary end point (i.e. pharyngeal cure rate), and adverse events. If after 25 subjects, the cure rate is $\leq 44\%$ (99% CI 17% – 74%; i.e. 11 persons of 25 persons with a positive culture on treatment date fail treatment), we will stop the study. We chose these numbers using the O'Brien-Fleming method of alpha spending for multiple analyses, assuming an alpha of 0.003 for the first analysis and an alpha of 0.049 for the final analysis. Using the 99% CI obtained with 11/25 treatment failures, the upper bound is less than 75%. Alternatively, if at interim analysis 32% or more of subjects (99% CI 9.4% - 63%) have a greater than 40% increase in their creatinine from baseline, we will halt the study.

Appendices

- A. Clinician Information and Referral Script
- B. Study Info Card
- C. Appointment Reminder Card
- D. Screening Eligibility Form
- E. Enrollment visit data entry form
- F. TOC visit data entry form

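### The interim renal halting rule is stated with two different triggers (more than 20%, and 32% or more) and two different numbers of looks, and nothing says which governs

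*Combined protocol and SAP*

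**What the plan says.** Three sections of the current text give a numeric renal rule. Each counts subjects whose creatinine rises by more than 40%.

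- **Statistical Analysis Plan in the summary:** "If more than 20% of the study population has a" rise of that size, the study halts. The reason follows: "We chose 20% because if 20% of subjects experience renal toxicity it is unlikely to be due to chance (95% CI 7 – 40"%).
- **Data Safety and Monitoring Plan, Data Analysis Plans:** the study halts "if at interim analysis more than 20% of subjects (99% CI 20% - 46%) have a greater than 40% increase in their creatinine from baseline".
- **Data Analysis, closing paragraph of Analyses:** the study halts "if at interim analysis 32% or more of subjects (99% CI 9.4% - 63%) have a greater than 40% increase in their creatinine from baseline".

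The number of looks also varies:

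- The summary has one: "We will conduct an interim analysis after we have primary outcome results for 25 subjects".
- Monitoring Procedures agrees, with review of "efficacy and renal toxicity and AEs in aggregate on at a single interim analysis after 25 subjects, and at the end of the study".
- Data Analysis Plans has two: "The Medical Monitor will conduct interim analyses after we have primary outcome results for 10 and 25 subjects".
- The Data Analysis section also has two: "we will conduct interim analyses after we have primary outcome results for 10 and 25 subjects".

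The two-look sections apply the renal rule at interim analysis without saying whether the look at 10 subjects is included. No section is said to take precedence.

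**The concern.** Renal safety is a stated aim, and this is the only numeric renal stopping rule for a 360 mg dose of gentamicin. If the observed proportion lies above 20% but below 32%, the Medical Monitor's action depends on which section is open. Choosing the threshold after seeing the count would defeat the purpose of fixing it in advance.

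The split on looks does not follow the split on thresholds: the more-than-20% trigger appears once with one look and once with two. Settling the trigger therefore does not settle the schedule.

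**Working it through.** **Inputs.** Triggers and looks are as quoted. The interim alpha of 0.003 is in Data Analysis Plans and in the Data Analysis section. Two things are assumed: 25 subjects with both creatinine values at the look, and true rates p of 5% to 40%, because the documents give no expected rate.

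**Step 1: the printed intervals.** Exact (Clopper-Pearson) limits for x events in n are the α/2 quantile of Beta(x, n−x+1) and the 1−α/2 quantile of Beta(x+1, n−x).

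| Where printed | Printed | Recomputed |
|---|---|---|
| Summary | 95%: 7 to 40% | 5/25, exact 95%: 6.8 to 40.7% |
| Data Analysis | 99%: 9.4 to 63% | 8/25, exact 99.7%: 9.4 to 63.2%; exact 99%: 11.35 to 59.52% |
| Data Analysis Plans | 99%: 20 to 46% | 5/25, exact 99%: 4.6 to 47.0%; 6/25, exact 99%: 6.6 to 51.4% |

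The first reproduces to within rounding. The second reproduces at the level that matches alpha 0.003, not at its 99% label. The third fits neither count. The normal-approximation 99% interval for 6/25 is 0.24 ± 2.576 × √(0.24 × 0.76/25) = 2.0 to 46.0%, so the printed 20% may be 2.0% with the decimal point lost.

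The 20% and 32% figures thus come from separate calculations, on 5/25 and 8/25. They are not one rule rounded in two ways.

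**Step 2: trigger counts.** At n = 25, 5/25 is exactly 20% and does not exceed it, so more than 20% means 6 or more. Because 8/25 = 32%, the other trigger means 8 or more. The sections differ at 6/25 (24%) and 7/25 (28%). At n = 10 the counts are 3 or more and 4 or more, so they differ at 3/10.

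**Step 3: one look at 25.** With X ~ Binomial(25, p), the halting probabilities are P(X ≥ 6) and P(X ≥ 8). Their difference, P(X = 6 or 7), is the chance that the sections disagree.

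| True rate p | P(X ≥ 6) | P(X ≥ 8) | P(X = 6 or 7) |
|---|---|---|---|
| 5% | 0.1% | <0.1% | 0.1% |
| 10% | 3.3% | 0.2% | 3% |
| 20% | 38% | 11% | 27% |
| 30% | 81% | 49% | 32% |
| 40% | 97% | 85% | 12% |

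**Step 4: if the look at 10 also counts (an assumption).** Halting then means X₁₀ ≥ 3 or X₂₅ ≥ 6 under the lower trigger, and X₁₀ ≥ 4 or X₂₅ ≥ 8 under the higher. The probability is 1 − Σ P(X₁₀ = x) · P(X₁₅ ≤ c − 1 − x), where X₁₅ counts events in the next 15 subjects. The sum runs over the values of x that do not halt at 10, and c is 6 or 8.

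| True rate p | More than 20% | 32% or more |
|---|---|---|
| 10% | 8.7% | 1.4% |
| 20% | 48% | 18% |
| 30% | 85% | 56% |
| 40% | 98% | 88% |

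**The case against.** A reader might infer that the protocol gives opposite instructions at 6 or 7 events. The text does not go that far. Each section states a condition that is enough to halt, and the Data Analysis section never orders continuation below 32%. A Medical Monitor who honoured every printed rule would halt above 20%. That stands. Even so, the 32% rule reads as a complete threshold, and someone working from that section alone would have no reason to halt at 7 of 25.

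A reader might also take the printed 20% lower limit in Data Analysis Plans to mean that lower rates are excluded once the trigger is met. The halting condition is the trigger, not the interval, and the figure may be a misprint or an artefact of reading the PDF. It needs correcting, but no argument should rest on it. The 99% label on the 8/25 interval is likewise a labelling matter that changes no decision.

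The true rate may also be low. Subjects with renal disease, diabetes or nephrotoxic drugs are excluded, and at a true 5% the sections would disagree about once in a thousand trials. That limits the likely impact.

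Finally, there are safeguards. The principal investigator and co-investigator review data and adverse events in real time, the two-look sections pause enrollment for the analyses, and the Medical Monitor may recommend stopping. These reduce the harm, but do not say which trigger applies.

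**Conclusion.** The inconsistency is real, lies in current text, and should be fixed before the first interim look. At 6 or 7 creatinine rises in 25, two sections require halting and a third does not. It is also unclear whether the rule operates at 10 subjects.

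The effect is small at true rates of 10% or below and large at 20% to 30%, where the choice of trigger moves the one-look halting probability by 27 to 32 percentage points. These sizes assume 25 creatinine pairs and independent subjects with a common true rate. They describe the numeric rule only, not the Medical Monitor's wider discretion. The disagreement does not depend on exactly 25 pairs: any observed proportion above 20% and below 32% falls in the gap.

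**What to change.** Put one identical sentence in the summary Statistical Analysis Plan, Data Analysis Plans and the Data Analysis section, and align Monitoring Procedures on the number of looks:

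> At each interim look, the study will be halted if more than 20% of treated subjects with both creatinine values (6 or more of 25; 3 or more of 10 if that look is kept) show a creatinine rise above 40%.

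This keeps the more cautious trigger, which appears in two sections and is the only one with a stated rationale. If the investigators and Medical Monitor prefer 32%, they should justify it and use it throughout. Naming the denominator is useful because the looks are timed by primary-outcome results, so the number of creatinine pairs need not be exactly 25.

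Print the exact interval of the triggering count at its true level (for 6/25, 99% CI 6.6 to 51.4%).

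The cost is wording only, with no added subjects, visits or assays. The downside is more halting at a true 10% rate than with the 32% trigger: 3.3% against 0.2% with one look, and 8.7% against 1.4% with two.

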APPENDIX A

Clinician Informational and Referral Script for The Gent Study

RN or Clinician: You have gonorrhea in your throat. We are conducting a study about a new medication for pharyngeal gonorrhea. Are you interested in learning more?

Patient: No

[figure not shown]
End of discussion

OR

Patient: Yes. What does it entail?

RN or Clinician: Great. I can just give you an overview, but instead of our usual treatment, you will get a different injection called gentamicin. Then you'll have to come back in about a week for a visit to make sure that you cleared the infection. You will earn up to \$XXX for participation. If you are still interested, I will call the study coordinator to come get you started.

APPENDIX D

Eligibility Screening Form

From Pre-screening Chart Review:

Pharyngeal Gonorrhoea Positive? Y or N

Date of Pharyngeal gonorrhoea test: _____

Chlamydial infection? Y or N (*If yes, patient not eligible*)

Syphilis infection? Y or N (*If yes, patient not eligible*)

Researcher: Is it alright with you if I ask you some questions in order to assess your eligibility for the study? Some of the questions are personal in nature.

Yes No

If the potential subject answers yes above, complete the following questions. Please check the boxes at left to indicate the question has been asked. Answer the question to the Right. Eligibility criteria are in italics following the question. You may stop the interview if, based on a single question, they do not meet eligibility criteria

Are you 16 years old or older? Yes

Do you speak and read in English? Yes

Have you taken any antibiotics (e.g. Keflex, bactrim, penicillin etc) in the past 30 days? Y or N (*If yes, they are not eligible*)

Are you allergic to any antibiotics? If so, which ones? _____ (*Allergy to gentamicin, spectinomycin, kanamycin, netilmycin, streptomycin, amikacin or tobramycin is an exclusion criteria.*)

Do you have kidney disease? Kidney diseases include renal failure (including dialysis); diagnosis of solitary kidney, renal cell carcinoma etc. (*Report of any renal disease is cause for exclusion.*)

Do you have Diabetes? Y or N (*Patients with diabetes are not eligible*).

Do you have a history of hearing loss or tinnitus? Y or N (*Patients with these symptoms are ineligible*).

What medications do you take on a regular basis? (*Potentially nephrotoxic drugs such as, Lisinopril, lithium and muscle relaxants, are cause for exclusion. If questions about certain drugs, call study PI.*)

List Here:

Are you able to return to the PHSKC STD Clinic in 4-7 days for a TOC visit? (Yes)

Study personnel:

In your estimation is the potential subject able to comply with the study procedures? Yes

Study personnel conducting screening: _____

If female-bodied patient, do urine pregnancy test. Record result here: Positive Negative

Ineligible if pregnant.

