This study consists of two study visits. Once enrolled, subjects need to return 4-7 days (+/- 1day) for a test of cure (TOC) visit. At their enrollment visit, the subject will set up a TOC visit with either the study coordinator or study clinician, hand them an appointment reminder card (see Appendix C). Less than 24 hours prior to the appointment, the study coordinator will call the patient with an appointment reminder call. If the subject does not show up for their appointment, the study coordinator will call them that day to set up another TOC visit appointment.

Study Procedures

Screening & Enrollment

Pre-screening will occur by the PHSKC STD Clinic RN who reviews all patients charts to determine which services and provider(s) are warranted. Patients with untreated pharyngeal gonorrhea will be referred to the study coordinator for screening. Screening will occur in person by the study coordinator, study clinician or PI. We will use a standardized screening eligibility form (see Appendix D) to determine patient's eligibility. Since eligibility hinges on a diagnosis of untreated pharyngeal gonorrhea, for PHSKC STD Clinic patients, we will ask the IRB for a waiver of consent to be able to pre-screen charts to access the subject's medical record to confirm diagnosis prior to approaching the patient. All other eligibility criteria will be based on self-report. Patient will be excluded if they meet any of the following criteria:

- Age less than 16 years
- Receipt of antibiotics in ≤ 30 days
- Known allergy to any aminoglycoside
- History of renal disease (including diagnosis of solitary kidney, chronic renal insufficiency, renal cell carcinoma etc),
- Use of concurrent nephrotoxic drugs or muscle relaxants
- History of diabetes
- History of hearing loss or tinnitus
- Concurrent infection with syphilis or chlamydia
- Pregnancy and/or nursing (we will screen women not using highly active birth control, i.e. OCPs, IUD or nexplanon, who are more than 28 days from their last menstrual period)
- Unable to return for a follow-up visit 4-7 days (+/- 1 day).
- Study team's discretion

Once it has been determined that the patient is eligible for and interested in the study, the study team member will go through the informed consent with the patient in detail. After the subject has signed the informed consent, formal study procedures will begin.

1. Intake & Data Entry Form:

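### Appendix D does not match the safety exclusions it applies, most clearly on medicines, so people the protocol excludes could pass screening

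*Combined protocol and SAP*

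**What the plan says.** The same exclusion list stands at the front of the protocol (Exclusion criteria, after the specific aims) and again under Study Procedures, Screening & Enrollment. Three of its items concern drug and renal safety: "Use of concurrent nephrotoxic drugs or muscle relaxants", "History of renal disease" (with examples) and "Known allergy to any aminoglycoside".

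Screening & Enrollment then says how the list is applied: "We will use a standardized screening eligibility form (see Appendix D) to determine patient's eligibility". Apart from the gonorrhoea diagnosis, "All other eligibility criteria will be based on self-report".

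Appendix D puts the three items to the patient as follows:

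- Medicines: "What medications do you take on a regular basis". A note to staff gives examples of excluding drugs and says to call the investigator if a drug is in doubt.
- Kidney: "Do you have kidney disease". The item goes on to name several diagnoses, ends the list openly, and tells staff that any renal disease reported is a reason to exclude.
- Allergy: an open question about allergy to any antibiotic, asking which. The note to staff reads "Allergy to gentamicin, spectinomycin, kanamycin, netilmycin, streptomycin, amikacin or tobramycin is an exclusion criteria".

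**The concern.** When eligibility is settled by a form filled from the patient's answers, the wording of the form is in effect the criterion. If a question is narrower than the exclusion behind it, an honest answer can leave an excluded person looking eligible. These three exclusions protect people receiving a drug whose renal safety the study itself sets out to evaluate (Aim 2), so what is at stake is mainly subject protection. There is also a consistency problem: staff who follow the form and staff who follow the protocol text could classify the same patient differently.

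**Working it through.** The plan gives no figure on this point, and no arithmetic applies to the mismatch itself. The check is a comparison of each exclusion with its item on the form, and then of what else stands between screening and injection.

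**Medicines.** The exclusion turns on concurrent use. The form asks about regular use. A drug taken as needed, or for a few days, is concurrent but need not be regular, so the question does not elicit it. The advice to call the investigator helps only with drugs the patient has already named. This mismatch is clear.

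**Kidney.** The exclusion is a history, and the question is in the present tense. The form's own hearing and tinnitus item does ask about history, so the difference in tense is not a house style. Chronic renal insufficiency is named in the exclusion but not on the form, although the form does name renal failure and leaves its list open. The gap that remains is past, resolved disease that the patient does not think to volunteer.

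**Allergy.** The question is as wide as the exclusion, or wider. The scoring note is not: it gives seven names with no catch-all, while the exclusion covers the whole class. An allergy to an aminoglycoside outside the seven would be written down, but the note would not mark it as excluding.

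**Same comparison, other items.** The exclusion for past or present diabetes is also asked in the present tense. Nursing is an exclusion, but the form provides only for a pregnancy test. The point does not rest on these two, but the same revision would cover them.

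**Later steps, in the protocol's order.**

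1. Intake (Study Procedures, step 1, and Appendix E) records current medicines, not limited to regular ones, and medical history. It comes after consent and before treatment, which is step 3. Neither the text nor Appendix E says these entries are compared with the exclusions.
2. Creatinine (Study Procedures, step 2) is first drawn 30, 45 or 60 minutes after the injection. Under Laboratory Processing the sample is then frozen and sent in monthly batches. It cannot reveal a missed renal exclusion before dosing.

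So the information that would close the medicines gap is collected in time, but no instruction puts it to that use.

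**The case against.** The strongest reply is that the form does not work alone. Screening is done in person by the coordinator, the study clinician or the investigator. The study team may exclude at its discretion. Intake asks about current medicines before the injection. The oversight section gives a named role the duty of assuring that all subjects meet the eligibility criteria. All of this is in the documents, and an attentive clinician could catch the cases described. It limits the point to a possibility. It does not remove it, because discretion needs information that the form does not ask for, and the protocol nowhere says that the intake entries are to be read against the exclusions.

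The reply is also right on two items. The kidney item must be read whole: its list of diagnoses and its instruction on any renal disease cover most of the exclusion. The allergy question is not narrow. Only its scoring note is.

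Three stronger readings are tempting, and the documents do not support them:

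- *Excluded people are dosed.* The text shows only that they could pass the form. Intake still lies between screening and injection.
- *A known share of the 60 subjects would be wrongly enrolled.* The documents give no rate for as-needed or short-course use, and none for how often intake would miss it.
- *The renal halting rule would be affected.* At 25 subjects, more than 20% means more than 0.20 × 25 = 5, so at least 6 (front-section Statistical Analysis Plan and the Data Analysis Plans of the monitoring section). A threshold of 32% means 0.32 × 25 = 8 (Data Analysis). If, purely as an assumption, 5% to 15% of subjects were missed users, that is 0.05 × 25 = 1.25 to 0.15 × 25 = 3.75 people. Even if every one had a qualifying creatinine rise, they alone would reach neither count.

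**Conclusion.** The form and the exclusion list disagree and need to be reconciled. One mismatch is clear (medicines) and two are lesser (the tense of the kidney question and the closed list for scoring allergies). Followed as written, Appendix D could pass people the protocol excludes. The conclusion rests on two readings of the text: that the form is the instrument that decides eligibility, which the protocol states, and that intake entries are not formally checked against the exclusions, since no such check is described. The number of people affected cannot be estimated from the documents, and no effect on the efficacy or renal results is claimed. The change is still worth making, because it concerns subject safety, no laboratory result is available before dosing, and the remedy is cheap.

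**What to change.** Reconcile both copies of the exclusion list with Appendix D so that the form asks about each exclusion in the protocol's own terms:

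- all medicines in concurrent use, not only regular ones;
- renal disease, past or present;
- allergy scored against any aminoglycoside, with the named drugs kept as examples only.

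If the team intends the narrower wording for any item, the exclusion list should be changed instead. Which wording is clinically right is for the team to decide.

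Add one sentence to Study Procedures, and a tick-box to Appendix E, stating that the intake medication and medical history entries are checked against the exclusions before the injection.

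The cost is a form revision and slightly more screen failures. No new visit, test or change in sample size is needed.
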